## 1.1.1. Disease and Study Drug Background

Osteoporosis is a systemic skeletal disease characterized by low bone mass and microarchitectural deterioration of bone tissue that leads to enhanced fragility and increased risk of fractures (Rizzoli 2001). This disease is characterized by low BMD and fractures. The fractures associated with the greatest morbidity and mortality, as well as economic burden to society, together make up the clinically significant and medically relevant group termed major osteoporotic fractures. In the US, there are an estimated 2 million osteoporotic fractures annually (Litwic 2014). The number of osteoporotic fractures is projected to increase in both men and women by more than 3-fold over the next 50 years as a result of the aging population (WHO 2007).

Spinal fractures have also been associated with poor outcomes and high mortality rates (Suzuki 2008). It has been reported that once a patient had sustained a vertebral fracture, the risk of a subsequent vertebral fracture increases by >300% and the risk of a subsequent hip fracture increased by 200% (Black 1999). Additional studies have shown that almost half of the patients with a prior vertebral fracture will experience additional vertebral fractures within 3 years, many within the first year (Robinson 2002; Lindsay 2001). Those patients who sustained a vertebral body fragility fracture showed a prolonged course that can lead to significant disability even one year later (Suzuki 2008). Patients with a diagnosis of osteoporosis who have had any fracture have an 86% increase in their risk for another fracture (Kanis 2004). With the severity of these implications, prevention of a secondary fracture has become a primary focus from a patient care and societal standpoint.

Major osteoporotic fractures (those of the wrist, shoulder, hip and clinical spine) account for 94% of the fracture risk for women with low or minimal trauma (Ensrud 2016). Major osteoporotic fractures contribute to accumulated frailty such that the Frailty Index is significantly larger in those elderly women who have experienced a major osteoporotic fracture. As a result, these women have worsening frailty and greater morbidity after a major osteoporotic fracture (Li 2015). The Frailty Index was associated with a predicted increase in the risk of falls, fractures, death and overnight hospitalizations (Li 2014). Consequently, prevention of clinically significant and medically relevant major osteoporotic fractures will reduce health care costs and benefit

postmenopausal women due to reduced frailty, reduced risk of falls, fractures, hospitalizations and death.

Bone remodeling occurs through the action of osteoclasts, which are involved in the resorption of bone followed by the formation of new bone by osteoblasts. In addition to continued use of calcium and vitamin D, the current therapeutic approach to the treatment of osteoporosis through inhibition of bone resorption includes agents such as bisphosphonates (Rosen 2005), or the monoclonal antibody denosumab, that inhibits the action of osteoclasts by binding to receptor activator of nuclear factor kappa-B ligand. An alternative approach has been to tip the balance between osteoblastic bone formation and osteoclastic resorption through the use of parathyroid hormone receptor modulation using teriparatide (rhPTH[1–34]).

Until recently, teriparatide has been the only approved osteoporosis treatment in which the major mode of action is stimulation of bone formation (anabolic) rather than suppression of bone resorption. The efficacy of teriparatide has important limitations related to its delayed and modest effects on increasing BMD at the total hip and femoral neck; and decreasing BMD at the distal 1/3 radius. The increase in cortical porosity that can occur may result in maladaptive effects on cortical bone microarchitecture (Bilezikian 2007). Abaloparatide has been evaluated in a number of nonclinical and clinical studies for its potential as a novel treatment for osteoporosis. Based on the biology of the PTH1 receptor signaling pathway, abaloparatide was designed to have less resorptive and hypercalcemic effects than PTH, resulting in a greater net anabolic effect.

## 1.1.2. Study Drug Development

## 1.1.2.1. Nonclinical Studies

A comprehensive nonclinical program including dermal tolerance, dermal sensitization, and general toxicology studies have been conducted in multiple species (rat, guinea pig, rabbit, minipig and monkey) for abaloparatide-SC and is considered supportive for abaloparatide-sMTS. Additionally, dermal tolerance, dermal sensitization, and general toxicology studies with abaloparatide-sMTS are ongoing or planned. The findings from the completed studies support the conclusion that abaloparatide-sMTS is well tolerated, with no new significant safety risks identified as compared to abaloparatide-SC. Full details of the nonclinical development program for abaloparatide are provided in the Investigator's Brochure (IB).

## 1.1.2.2. Clinical Studies

There are 19 completed or ongoing clinical studies which comprise the abaloparatide-SC (subcutaneous) and the abaloparatide-sMTS (transdermal) clinical development programs. The abaloparatide-SC clinical trial program consists of 11 completed clinical trials, including a large pivotal Phase 3 study (BA058-05-003) followed by an open-label extension (BA058-05-005).

The abaloparatide-sMTS clinical trial program consists of 4 completed Phase 1 and Phase 2 studies, and an ongoing Phase 1 study (BA058-05-015) to select an optimized formulation and dose for abaloparatide-sMTS to be used in the Phase 3 study.

Additional details for the completed clinical studies and the ongoing study BA058-05-015 can be found in the most recent IB.

## 1.1.2.2.1. Abaloparatide-SC

In the pivotal Phase 3 study (BA058-05-003, the ACTIVE trial), 2,463 postmenopausal osteoporotic women were randomized to receive daily 80  $\mu$ g abaloparatide-SC (n=824), placebo (n=821), or teriparatide 20  $\mu$ g (n=818) (rhPTH 1-34) for 18 months. In this trial, abaloparatide-SC and teriparatide significantly reduced the risk of new morphometric vertebral fractures, by 86% and 80%, respectively, compared to placebo. Abaloparatide-SC significantly reduced nonvertebral, major osteoporotic and clinical fractures compared to placebo. Compared to teriparatide, abaloparatide significantly reduced major osteoporotic fractures. The Kaplan-Meier plots indicate an early and sustained fracture risk reduction of nonvertebral, major osteoporotic and clinical fractures with abaloparatide-SC treatment. Abaloparatide-SC was generally safe with acceptable tolerability in postmenopausal women with osteoporosis; the most common adverse reactions (incidence  $\geq$  5%) were hypercalciuria, dizziness, nausea, headache and palpitations. Consistent with reduced abaloparatide-SC-mediated calcium mobilization, the rates of hypercalcemia were lower in the abaloparatide-SC group compared to the teriparatide group.

In the ACTIVExtend trial (BA058-05-005), subjects who were in the abaloparatide-SC or placebo arms were transitioned to oral alendronate 70 mg weekly. Subjects who received 18 months of abaloparatide-SC followed by 6 months of alendronate experienced no new morphometric vertebral fractures from the BA058-05-005 study baseline and continued to have statistically significant reductions in nonvertebral, major osteoporotic, and clinical fractures when compared to subjects who previously received 18 months of placebo followed by 6 months of alendronate. These results validate the osteoporosis treatment paradigm of build (with an anabolic agent), and then maintain and consolidate gains (with an anti-resorptive agent).

Abaloparatide-SC demonstrated an increase in BMD at the lumbar spine, total hip, femoral neck and ultradistal radius in osteoporosis subjects, consistent with the fracture risk reduction. The results from the ACTIVE trial and the first 6 months of the ACTIVExtend trial, together with the entire data set from the abaloparatide-SC development program, support the safety and efficacy of abaloparatide-SC for the reduction of fractures in postmenopausal women with osteoporosis.

In Study BA058-05-005, after 25 and 43 months of treatment (18 months abaloparatide, 1-month transition, followed by 6 or 24 months of alendronate, respectively), the reductions in new vertebral fracture for abaloparatide/alendronate vs placebo/alendronate-treated subjects show long-term vertebral fracture reduction of 90% after 25 months and 84% after 43 months. In the ACTIVExtend trial the AEs were comparable between subjects previously treated with abaloparatide-SC and the previous placebo group.

There have been no cases of osteosarcoma, osteonecrosis of the jaw or atypical femoral fracture in the entire abaloparatide-SC clinical development program. In non-clinical studies, a dose dependent incidence of osteosarcomas was seen in both male and female rats treated with abaloparatide- and in a positive control group treated with hPTH (1-34).

Overall, the clinical results of abaloparatide-SC-mediated early vertebral and nonvertebral fracture risk reduction and increases in BMD are consistent with the known anabolic mechanism of action, changes in bone turnover markers and nonclinical results.

## 1.1.2.2.2. Abaloparatide-sMTS

To date, several different abaloparatide-sMTS formulations have been evaluated in a total of 4 Phase 1 studies and 1 Phase 2 study, including an abaloparatide-sMTS PBS formulation (abaloparatide phosphate buffered saline [PBS]) and an optimized formulation (abaloparatide ZnCl2·HCl).

The abaloparatide-sMTS PBS formulation had similar abaloparatide  $C_{max}$  but lower abaloparatide AUC than the abaloparatide-SC 80  $\mu g$  reference treatment. This abaloparatide-sMTS formulation was evaluated in 3 completed Phase 1 studies in healthy postmenopausal women (BA058-05-004, BA058-05-006 and BA058-05-008). An overview of the design of these studies is provided in Figure 1. These studies were conducted to evaluate the PK, safety, and local tolerability of different doses of abaloparatide-sMTS and to evaluate the impact of the application site and the duration of application (wear time) on PK, safety, and local tolerability.

A Phase 2, dose-range-finding study, Study BA058-05-007, was also conducted with the abaloparatide-sMTS PBS formulation to evaluate the PK, efficacy, and safety of 3 doses of abaloparatide-sMTS (50, 100, and 150  $\mu$ g) compared to 80  $\mu$ g abaloparatide-SC and placebo-sMTS in postmenopausal women with osteoporosis. An overview of the study design is provided in Figure 1. The results from this study did not support the selection of this abaloparatide-sMTS PBS formulation for further clinical development, although it did provide important insights into the exposure-response relationship between abaloparatide-sMTS and increases in BMD.

BA058-05-015 was a Phase 1 study initiated to select an optimized formulation and dose for abaloparatide-sMTS to be used in the Phase 3 study. From the pharmacokinetic data in this clinical study, it was determined that abaloparatide-sMTS Formulation W-1 (Abaloparatide: ZnCl2 , HCl ) 300  $\mu$ g applied to the thigh for 5 minutes provides a single patch administration option with a similar PK profile (slow absorption with a similar time of maximum observed plasma concentration [tmax] and AUC) to abaloparatide-SC 80  $\mu$ g and is expected to produce similar pharmacodynamic effects on BMD as the marketed abaloparatide-SC 80  $\mu$ g treatment in the clinical setting. Additionally, abaloparatide-sMTS Formulation W-1 300  $\mu$ g applied to the thigh for 5 minutes had an acceptable safety profile in the BA058-05-015 study.

Full details of the results of clinical trials conducted with abaloparatide-SC and abaloparatide-sMTS are provided in the IB.

## 1.2. Study Rationale

The purpose of this study is to evaluate the ability of subjects to self-administer 300 µg abaloparatide-sMTS over a period of 29 days based on analyses of pharmacokinetic (PK) and pharmacodynamic (PD) markers. The systemic exposure will be compared to historical exposure after treatment with abaloparatide SC as well as results from BA058-05-015,

Cohort 7, where subjects were treated with the same product as a single dose by a trained healthcare professional.

## 1.3. Dose Rationale

The dose of 300  $\mu$ g of abaloparatide-sMTS, applied to the thigh for 5 minutes, was chosen based primarily on the comparability of its pharmacokinetic profile to that of the approved drug abaloparatide SC at 80  $\mu$ g per day as was demonstrated in study BA058-05-015.

## 2. STUDY OBJECTIVES AND ENDPOINTS

## 2.1. Objective

The primary objective of this study is to evaluate the ability of subjects to self-administer 300  $\mu g$  abaloparatide-sMTS over a period of 29 days based on pharmacokinetic (PK) and pharmacodynamic (PD) markers.

## 2.2. Primary Endpoint

The primary endpoint is the systemic exposure of the drug at Day 1, Day 15 and Day 29.

## 2.3. Secondary Endpoints

## 2.3.1. Pharmacodynamic (PD) Endpoints

- Percent change of s-PINP from baseline to Day 15 and Day 29.
- Change and percent change in serum calcium (albumin-corrected) from baseline to each post-dose timepoint.
- Change and percent change in serum phosphorus from baseline to each post-dose timepoint.
- Change and percent change in cAMP from baseline to each post-dose timepoint.

## 2.3.2. Other Endpoints

- Subject satisfaction and convenience of treatment as measured by Treatment Satisfaction Questionnaire for Medication (TSQM9) at Day 15 and Day 29
- Subject acceptability measurement (5-point Likert Scale) at Day 1, Day 15 and Day 29
- Subject preference for treatment attributes at Day 1, Day 15 and Day 29
- Investigator assessment of signs of local skin reaction using a 4-point scale at Day 1, Day 15 and Day 29
- Subject assessment of symptoms of local skin reaction using a 4-point scale from Day 1 through Day 29 as recorded in the subject diary
- Daily measurement of user errors as recorded in the subject diary
- Daily measurement of patch adhesion as recorded in the subject diary.

## 2.3.3. Safety and Tolerability Endpoints

AEs, vital signs (orthostatic blood pressure, pulse rate, body temperature, and respiration rate), ECG, and laboratory tests (serum chemistry, hematology, coagulation, and urinalysis) will be assessed as per the schedule of assessment (SOA) (Table 1).

## 3. STUDY DESIGN

[figure not shown]
## 3.1. Description of the Study Design

This is an open-label study to evaluate the usability of the abaloparatide-sMTS by subjects with low BMD. The study will consist of a Screening Period (up to 2 months), a Pre-Treatment Period (1 week), a Treatment Period (1 month), and a 1 week Follow-Up after the last dose of study medication. Thus, subjects will be in the study for up to 4 months. Eligible subjects will undergo protocol specified procedures, including BMD (if dual energy x-ray absorptiometry [DXA] was done over 12 months prior to Screening) and bone turnover marker assessment. For the purpose of this study, 1 month is equivalent to 30 days.

All eligible subjects will be provided calcium and vitamin D to ensure that their daily intake is 1,200 mg/day and 800 IU/day, respectively, or a dose determined by the Investigator and agreed by the Sponsor Medical Monitor, according to the subject's need.

All subjects will undergo safety, pharmacokinetic, bone turnover marker (s-PINP), and assessments of User Errors and Subject Preference Outputs according to the SOA (Table 1). The study design is presented in Figure 1, below.

Figure 1: Study Design

## 4. SELECTION OF STUDY POPULATION

In order to participate in this study, a subject must meet all of the following inclusion criteria and none of the exclusion criteria. Subjects who were screened and excluded from this study will be recorded in the eCRF with the reason for the screen failures.

## 4.1. Inclusion Criteria

Subjects must meet all of the following inclusion criteria:

- 1. Healthy ambulatory female from 50 to 85 years of age (inclusive).
- 2. Postmenopausal for at least 2 years. Postmenopausal status will be established by a history of amenorrhea for at least 2 years, negative serum pregnancy test or an elevated serum follicle-stimulating hormone (FSH) value of  $\geq$  30 IU/L.
- 3. BMD T-score based on the female reference range of <-1.0 and >-5.0 at the lumbar spine (L1–L4) or hip (femoral neck or total hip) by DXA. Note: Every effort will be made to enroll subjects with a T-score of -2.0 or lower but > -5.0; for those with scores higher than -2.0, preference should be given to subjects with lower BMD scores.
- 4. Good general health as determined by medical history and physical examination (including vital signs), has a body mass index of up to 33 kg/m2, and is without evidence of clinically significant abnormality that may increase the risk associated with study participation or investigational product administration, or may interfere with compliance or the interpretation of study results, and would make the subject inappropriate for this study in the opinion of the Investigator
- 5. Serum calcium (albumin-corrected), intact PTH, serum phosphorus, alkaline phosphatase, and thyroid stimulating hormone (TSH) values all within the normal range during the Screening Period. Subjects with minor elevations or reductions in serum calcium may be enrolled if serum ionized calcium is normal. Any subject with an elevated alkaline phosphatase value, and who meets all other entry criteria would be required to have a normal bone-specific alkaline phosphatase to be enrolled
- 6. Serum 25-hydroxyvitamin D values  $\geq 20$  ng/mL.
- 7. Resting 12-lead electrocardiogram at screening shows no clinically significant abnormality.
- 8. Systolic blood pressure is  $\geq 100$  and  $\leq 155$  mmHg, diastolic blood pressure is  $\geq 40$  and  $\leq 95$  mmHg, and heart rate is  $\geq 45$  and  $\leq 100$  bpm (taken sitting)
- 9. No clinically significant abnormality of serum hemoglobin, hematocrit, white blood cells, and platelets, or usual serum chemistry, including electrolytes, renal function, liver function and serum proteins, that might be expected to interfere with the subject's health and/or medical treatment during the study
- 10. Read, understood, and signed the written informed consent form
- 11. Hemoglobin value  $\geq$  12.0 g/dL

## 4.2. Exclusion Criteria

Subjects who meet any of the following exclusion criteria will be excluded from the study:

- 1. History of bone disorders (eg, Paget's disease) other than postmenopausal osteoporosis
- 2. History of prior external beam or implant radiation therapy involving the skeleton, other than radioiodine
- 3. History of Cushing's disease, hypo- or hyper-parathyroidism or malabsorptive syndromes within the past year
- 4. History of significantly impaired renal function (serum creatinine > 177 μmol/L or > 2.0 mg/dL). If serum creatinine is > 1.5 and ≤ 2.0 mg/dL, the calculated creatinine clearance (Cockcroft-Gault) must be ≥ 37 mL/min
- 5. History of any cancer within the past 5 years (other than basal cell or squamous cancer of the skin)
- 6. History of osteosarcoma at any time
- 7. History of nephrolithiasis or urolithiasis within the past 5 years
- 8. Application site (thigh) compromised by scars, inflammation or skin conditions to an extent that may compromise uniformity of abaloparatide-sMTS application or drug delivery (nevi, plaques, tattoos, scars, piercing, etc.)

## Medication-related exclusion criteria:

- 9. Known history of hypersensitivity to any of the test materials or related compounds
- 10. Prior therapeutic treatment with PTH- or PTHrP-derived drugs, or bone anabolic drugs including abaloparatide, teriparatide, or PTH(1-84). Subjects who received abaloparatide in prior Phase 1 studies are not excluded
- 11. Prior treatment with intravenous bisphosphonates at any time or oral bisphosphonates within the past year (12 months). Subjects who have received a short course of oral bisphosphonate therapy (3 months or less) may be enrolled as long as the treatment occurred 6 or more months prior to enrollment
- 12. Treatment with fluoride or strontium in the past 5 years or prior treatment with gallium nitrate or bone-acting investigational agents at any time
- 13. Prior treatment with calcitonin or tibolone in the past 6 months
- 14. Treatment with denosumab within the past 18 months
- 15. Treatment with anticonvulsants that affect vitamin D metabolism (phenobarbital, phenytoin, carbamazepine or primidone) or with chronic heparin within the 6 months prior to the Screening Period
- 16. Treated with anabolic steroids or calcineurin inhibitors (cyclosporin, tacrolimus) within the past 90 days.

17. Prior treatment with selective estrogen receptor modulators (except hormone replacement therapy) or daily treatment with oral, intranasal, or inhaled corticosteroids within the 12 months prior to the Screening Period. Occasional use of all corticosteroids (for seasonal allergies or asthma) is not exclusionary. Use of low dose oral corticosteroids (eg, ≤ 5 mg/day of prednisone or the relative equivalent dose of another corticosteroid) is also not exclusionary.

18. Participation in another clinical trial with any investigational drug or device within 3 months or 5 half-lives of the investigational drug (if known), whichever is longer, of study drug administration.

## Lifestyle-related exclusion criteria:

- 19. Abnormal nutritional status as assessed by the investigator including abnormal diets and excessive or unusual vitamin or herbal intakes; vitamin D intake of  $\geq$  4,000 IU/day or vitamin A intake of  $\geq$  10,000 IU/day. Short term use of high doses of vitamin D to bolster endogenous vitamin D levels for study entry during the screening period is not exclusionary
- 20. Active drug or alcohol dependence or abuse (excluding tobacco or medicinal or recreational marijuana use where legal unless there is evidence of abuse) within 12 months of the screening period; or evidence of such abuse (in the opinion of the investigator).

## 4.3. Subject Withdrawal or Termination

## 4.3.1. Reasons for Withdrawal or Termination

Subjects will be informed that they have the right to withdraw from the study at any time for any reason without prejudice to their medical care.

The Investigator may consider discontinuing subjects from the study for the following reasons:

- Severe hypersensitivity to abaloparatide or test materials
- Refusal of treatment
- Inability to complete study procedures
- Lost to follow-up
- Adverse events or laboratory abnormalities which, in the judgment of the Investigator, justifies treatment cessation
- Serious intercurrent illness
- Protocol violations
- Administrative reasons
- Incident vertebral or non-vertebral fragility fracture

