## 4.3.2. Handling of Subject Withdrawals or Terminations

If a subject is withdrawn or discontinued from the study, the reason for withdrawal from the study must be recorded in the source documents and on the case report form. All subjects withdrawn prior to completing the study should be encouraged to complete study procedures scheduled for the Visit 5 / end of treatment (EOT) (Day 29) visit as soon as possible. All AEs should be followed as described in Section 7. Subjects who discontinue or are withdrawn from the study will not be replaced. Whenever a subject is discontinued prematurely, the Sponsor and the Medical Monitor must be notified.

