## 4.7. Temporary Suspension of Treatment

Due to the short nature of the study, temporary suspension of treatment is not an option for the Investigator. Any subject that is deemed inappropriate for continuing treatment will be withdrawn from the study and the reason will be noted in the CRF.

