4.7.8.1 Summary of patch application by study day

- Frequency counts (and percentages) for the successful first application
- Frequency counts (and percentages) of the application location for the successful application
- Descriptive statistics for the time from removal from refrigerator until application – data from successful application is used
- Descriptive statistics for the time from patch application until removal – data from successful application is used

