4.7.8.3 Summary of patch application difficulties by study day

Frequency counts (and percentages) for items related to patch application difficulty will be provided using the available data collected at the study day

- Steps with difficulty
- Difficulty opening pouch
- Patch falls on floor
- Touch patch before application
- Difficulty caused by pain
- Difficulty caused by other issues

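### The SAP's usability tables may overstate sustained ability to self-administer, because no planned summary counts the days after a woman stops as unsuccessful when she cannot or will not apply the patch.

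*Protocol*

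**What the plan says.** **Objective.** Protocol 2.1 begins: "The primary objective of this study is to evaluate the ability of subjects to self-administer". The sentence goes on to base that evaluation on PK and PD markers, and Protocol 2.2 makes systemic exposure on Days 1, 15 and 29 the primary endpoint. Usability (user errors, acceptability, adherence) is a secondary objective in the synopsis, and diary-recorded user errors fall under the other endpoints in Protocol 2.3.2.

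**Stopping.** The list in Protocol 4.3.1 opens: "The Investigator may consider discontinuing subjects from the study for the following reasons". It includes refusing treatment and "Inability to complete study procedures"; administrative reasons are a separate entry. Protocol 4.7 rules out a pause: "Any subject that is deemed inappropriate for continuing treatment will be withdrawn from the study and the reason will be noted in the CRF". Protocol 4.3.2 adds that "the reason for withdrawal from the study must be recorded in the source documents and on the case report form" and that "Subjects who discontinue or are withdrawn from the study will not be replaced".

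**Usability tables.**
- By-day success (SAP 4.7.8.1) is given as "Frequency counts (and percentages) for the successful first application", with no denominator stated.
- By-day difficulty (SAP 4.7.8.3) is summarised "using the available data collected at the study day". The per-subject difficulty and by-day cleaning tables use the same wording.
- The per-subject success rate (SAP 4.7.8.2) is first-time successes divided by the applications that woman made.

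**Around them.** SAP section 4 makes the Safety Population the default set. SAP 3.9 includes non-completers in tables where appropriate. SAP 3.10 rules out imputation for PD and safety data and does not mention user-error data. SAP 4.1 tabulates women not completing all doses, and women discontinuing the study, each with reasons.

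**The concern.** In a usability study, a woman who gives up because she cannot or will not apply the patch is an informative failure. The protocol itself motivates its subject-reported measures by the high discontinuation seen with osteoporosis treatments (Protocol 6.6.5).

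The plan does not clearly capture that failure. One available reason covers any study procedure, so trouble with the patch can sit beside trouble with blood draws, visits or the diary. No usability summary has a rule for the days after she stops. Late-treatment percentages would then describe only the women still able to continue, and a reader could take them as the success rate of everyone who started. With about 22 women treated, one or two such exits would change the figure visibly.

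**Working it through.** **Inputs.** About 22 women are treated so that at least 18 complete (Protocol synopsis; Pharmacometric Analysis Plan 7.3). This implies an allowance of 22 − 18 = 4, or 4/22 = 18.2%. The plan gives no power calculation, dropout rate or usability target, so it has no figure to reproduce. Dosing runs from Day 1 to Day 29, which is 29 planned days. The number k of women who stop because they cannot or will not apply the patch is assumed, from 0 to 4. The documents give no rate.

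**By-day success at Day 29.** Let p be the success share among women still applying, and suppose nobody leaves for another reason.
- Available-data denominator: p.
- All-treated denominator, with stopped women counted as not successful: p(22 − k)/22.
- Difference: pk/22, which is 1/22 = 4.5 points per woman when p = 1.

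| k | Available data, p = 1 | All treated, p = 1 | Difference, p = 1 | Difference, p = 0.90 |
|---|---|---|---|---|
| 0 | 100% | 22/22 = 100% | 0 | 0 |
| 1 | 100% | 21/22 = 95.5% | 4.5 | 4.1 |
| 2 | 100% | 20/22 = 90.9% | 9.1 | 8.2 |
| 3 | 100% | 19/22 = 86.4% | 13.6 | 12.3 |
| 4 | 100% | 18/22 = 81.8% | 18.2 | 16.4 |

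The exact (Clopper-Pearson) 95% interval is 81.5–100% for 18/18 and 59.7–94.8% for 18/22. The plan gives no intervals for these tables; these only show how little 22 women can settle.

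**Mixed reasons for leaving.** Suppose 4 leave but only one because of the patch, and the other 18 succeed. The available-data figure is 18/18 = 100%. Setting aside the 3 who left for other reasons gives 18/19 = 94.7%. Counting all 4 as failures gives 18/22 = 81.8%, which would overcorrect. The reason for stopping therefore has to be known.

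**Per-subject success rate (assumed example).** A woman stops after 5 attempts, 3 of them successful first time.
- SAP 4.7.8.2 gives 3/5 = 60%.
- Over planned days the figure is 3/29 = 10.3%.
- With four such women and 18 at 100%, the mean is (18 × 100 + 4 × 60)/22 = 92.7% under the SAP, against (18 × 100 + 4 × 10.3)/22 = 83.7% over planned days.

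**Compliance behaves the same way.** SAP 4.3 divides doses received by the span from first to last dose. A woman who takes every dose on Days 1 to 5 and then stops scores 5/5 = 100%, against 5/29 = 17.2% of planned days.

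**The case against.** The case on the other side is substantial, and most of it narrows the point.

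- **The success table has no available-data rule.** That wording belongs to the difficulty and cleaning tables. SAP 4.7.8.1 names no denominator, and the default set is all treated women. A reader might infer that stopped women certainly leave the success percentage. The documents make that likely, from the neighbouring tables, but do not say it. The defect that can be stated as fact is an undefined denominator.
- **Failure need not lead to exit.** Discontinuation under 4.3.1 is at the investigator's discretion, retraining after Day 1 is allowed (Table 1, note 12), and damaged patches are replaced (Protocol 5.3). A woman who makes errors and stays is still counted with her failures.
- **Stopped women are not hidden.** Reasons go on the case report form, disposition is tabulated with reasons and listed by subject, diary entries give reasons for missed doses (Protocol 5.6), and counts accompany percentages. Refusing treatment already has its own entry, and the actual form is not in the documents, so it may be finer than 4.3.1.
- **They stay in the per-subject summary** for the attempts they made.
- **Success per application made is a legitimate measure.** Counting later days as failures answers a different, composite question.

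All of this stands. It does not supply a denominator, a patch-specific reason, or any figure for the share of treated women still applying successfully. The last argument weighs against replacing the planned percentage but not against adding a second one beside it.

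**Conclusion.** The point holds as a possibility, for the secondary usability tables only. If any woman stops because she cannot or will not apply the patch, SAP 4.7.8.1 to 4.7.8.4 do not count her later days as unsuccessful, and disposition may not identify her.

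At Day 29 the possible overstatement is about 4.5 points per such woman when all others succeed. It is zero if there are none and 18.2 points if the whole allowance of 4 stopped for this reason. The size rests on reading the by-day success percentage as available data and on an assumed number of such women. The top of the range is a worst case, because the 22-to-18 allowance covers loss for any reason.

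A reader might go further and conclude that the trial's main answer on self-administration is biased toward success. This point does not support that, because the primary endpoint is systemic exposure and does not use the diary percentages. The study is also descriptive, with no formal tests, so no decision threshold depends on these figures. A modest addition to the tables is enough.

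**What to change.** 1. In SAP 4.7.8.1, state the denominator of the by-day success percentage.
2. Beside the available-data percentage, give by-day success with the Safety Population as denominator. Count planned days after a stop for inability or unwillingness to apply the patch as not successful. Show women absent for other reasons on their own line, so that unrelated losses are not read as application failures.
3. Report the number and percentage of treated women who stopped for these reasons.
4. Record two distinct discontinuation sub-reasons, unable to self-apply the patch and unwilling to continue applying it, in Protocol 4.3.1 and on the disposition form, unless the form already separates them.

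This changes only what is recorded and tabulated. It does not alter who is withdrawn or retrained, adds no visits or procedures, and leaves the planned percentages in place. The cost is one extra column, a short summary line and a small form change. The one downside is that the reported success rate may look less favourable.
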